4.3.2.3 Intervention arm (FACT)

The FACT intervention is an interactive mobile responsive web application that provides personally tailored communication guidance to parents with cancer to help them talk about their illness with their minor children.

Upon accessing the mobile responsive web application, participants will be prompted to enter their study ID and then complete a tailoring assessment. The assessment addresses child and family characteristics, the participant's disease characteristics, their communication goals, communication concerns, and prior communication experiences. Using study-specific computer tailoring algorithms, the web application then provides the participant with customized communication feedback. Participants complete the tailoring assessment individually for each child for which they seek customized feedback, however, they will be asked to complete outcome measures in reference to one selected child. Throughout the study period, the participant can access the web application at a frequency, duration, and timing of their choosing and may re-take the assessment to receive updated information. They will not provide identifiable data via the web application but they can choose to save their data for later review. Participants will be informed that the research team will monitor user-log metadata (e.g., log ins, webpage views) and that the participant may incur data charges related to their use of the FACT web application based on their individual data plan.

Inclusion of participants for whom barriers to internet access exist

For participants who lack reliable home internet access, we will offer in-hospital use of a password-protected study tablet to access the intervention. These participants will have the opportunity to print their customized materials and/or re-use the study tablet during subsequent hospital visits.

Check-in phone call or message

No more than one week after a participant has received access to the online FACT portal, a member of the study team will contact the participant via their preferred communication method. This will serve the purpose of quickly identifying and resolving any login or other issues should a participant experience them.

Forced-response items

All tailoring items within the online intervention interface will be forced-response, as missing items would result in the being unable to generate participants' tailored materials. This will be clearly disclosed during the informed consent process and in informed consent documents as described above.

4.3.2.4 Control arm (Waitlist control)

Participants in the waitlist control condition will receive their usual care – which includes access to the UNC CCSP (for which the PI serves as the Deputy Director of Clinical Operations) by clinician- or self-referral. A waitlist control model allows the research team to collect maximally rigorous data while addressing the ethical considerations of completely withholding the study intervention from participants assigned to this arm.

These individuals will participate on the same schedule as the treatment arm but receive the study intervention after their data collection activities are complete. Given the elevated psychological distress that parents with cancer experience and the low risk profile of the protocol, use of a waitlist control group is appropriate.

4.3.2.5 3-Week Follow-up assessment (T1)

Participants will complete follow-up surveys via secure REDCap link or pen-and-paper.

4.3.2.6 6-Week Follow-up assessment (T2)

Participants will complete follow-up surveys via secure REDCap link or pen-and-paper.

The post-intervention semi-structured interview may be conducted in person at NCCH, by telephone, or by secure video. The interview content will ask participants to discuss barriers and facilitators to intervention use, desired communication content areas not addressed in the current communication tool (treatment arm only), feedback on their experiences communicating with their children, opinions on study procedures, suggestions for improvement to the intervention and/or study activities, and any psychosocial follow-up needs. The interview is expected to last approximately 30 minutes and will be conducted by a member of the study team with training in conducting such research interviews with patients. Participants are not required to answer questions they find emotionally distressing and are reminded of this right prior to beginning the interview. All interviews will be audiotaped and then transcribed for analysis.

4.3.3 EMR abstraction

Research team members will abstract basic data from the EMR about participants' eligibility, demographics, cancer and its treatment, and cancer support intervention use.

To facilitate screening procedures, research staff will obtain information about patients' parental status and cancer type and stage through review of the EMR. EMR data will be stored electronically on the REDCap database for the duration of study recruitment so that we do not re-contact individuals whom we have previously identified as ineligible or who decline study participation. Following the conclusion of study recruitment, this information will be destroyed. For participants who enroll in the study, research staff will additionally collect information on their cancer and its treatment and supportive care intervention use after obtaining HIPAA Authorization for research.

4.3.4 Intervention usage metrics

For participants in the intervention condition, the password-protected, mobile responsive web application created by CHAI (Connected Health for Applications and Interventions) Core at UNC will track user-log metadata such as number of user log ins, session duration and pages accessed. This data will be stored electronically on the CHAI Core at UNC secure server.

4.3.5 Self-report measures

Participants will complete several outcome measures. Participants may complete some or all of the surveys and can skip any questions they find distressing.

The measuring instruments, schedule of administration, and estimated duration are listed in Table 1.

Table 1. Measuring instruments

Domain	Measure	Time (min)	Arm	Schedule
Demographic form	Demographic form	2	Both	T0
Performance status	Eastern Cooperative Oncology Group Performance Status Scale (ECOG)	1	Both	T0
Illness beliefs	Two items, Investigator-designed, minimally adapted for this study	1	Both	T0
Parental cancer communication beliefs & behaviors	Parental Cancer Communication Questionnaire (PCCQ)	5	Both	T0, T1, T2
Anxiety symptoms	Generalized Anxiety Disorder – 7 (GAD-7)	3	Both	T0, T1, T2
Depression symptoms	Patient Health Questionnaire-2 (PHQ-2)	1	Both	T0, T1, T2
Communication self-efficacy	Communication Self-Efficacy Scale (CES-E)	3	Both	T0, T1, T2
Parent-child relationship	Single-item assessment, adapted from Sandler, et al.	1	Both	T0, T1, T2
Acceptability	FACT Satisfaction scale	3	Treatment	T1, T2
Other resource use	Investigator-designed, single item	1	Both	T0, T2

4.3.5.1 Demographic form

The investigator-designed demographic form (see Appendix A) is a brief self-administered questionnaire that includes questions such as age, race/ethnicity, education, family composition, and marital status. Based on the PI's prior studies, the average time to complete the measure is estimated to be 2-3 minutes.

4.3.5.2 Eastern Cooperative Oncology Group Performance Status Scale (ECOG)

The ECOG evaluates the severity of symptoms and amount of assistance the participant requires to complete "normal activities" using a 5-point scale (see Appendix B). The ECOG is used to assess how the disease affects the daily living abilities of the patient and determine appropriate treatment and prognosis.¹¹ It has been modified for patient self-report.

4.3.5.3 Illness beliefs

Two questions assessing participants' appraisals of illness severity, adapted from Compas, et al. (see Appendix B).¹²

4.3.5.4 Parental Cancer Communication Questionnaire (PCCQ)

Participants will be asked up to 26 investigator-designed questions assessing their parental communication concerns (appraisals), their beliefs about anticipated

consequences of discussions with their children about cancer (outcome expectancies), and their communication behaviors with their children. Parents who have engaged in any communication with their children about cancer will also be asked questions about their child(ren)'s response to these discussions (see Appendix C). The estimated time to complete these items is 5-7 minutes.

4.3.5.5 Generalized Anxiety Disorder – 7 (GAD-7)

The GAD-7 is a common measure of anxiety consisting of 7 items (Appendix D). The scale captures the elements of thoughts, emotions, and physical symptoms associated with general anxiety. The GAD-7 is very well-validated for the general population in addition to use for clinical assessment (e.g. psychiatric disorders). Items are scored on a four-point Likert scale with responses scores ranging from 0 (low/no anxiety) to 3 (high anxiety). Scores about 10 are considered to be clinically significant for anxiety.¹³ The estimated time to complete this measure is no more than 5 minutes.

4.3.5.6 Patient Health Questionnaire – 2 (PHQ-2)

The PHQ-2 is a brief, well-validated measure of severity of depression symptoms and is used extensively in clinical and research settings (Appendix E).¹⁴ Participants are asked to respond to 2 items, respectively measuring depressed mood and anhedonia, and indicate the extent to which they were bothered by that symptom in the two weeks prior to the questionnaire. Items are Likert-type and have response options of 0 ("not at all"), 1 ("several days"), 2 ("more than half the days"), and 3 ("nearly every day"). The estimated time to complete this measure is no more than 1 minute.

4.3.5.7 Communication Self-Efficacy Scale (CSES)

The nine-item CSES is adapted from Murphy et. al.'s maternal HIV disclosure self-efficacy scale¹⁶ (see Appendix G). Participants rate nine statements assessing their level of confidence in their ability to tell their child about their diagnosis using a visual analogue scale. This scale has been extensively used in the parental HIV communication literature. In prior studies the Cronbach's alpha for the scale was 0.90.

4.3.5.8 FACT Satisfaction scale

The intervention satisfaction assessment is composed of six investigator-designed question items assessing the relevance and acceptability of the study intervention (see Appendix H) and a single free text question for suggestions. Participants rate each item on a 4-point ordinal scale ranging from 0 to 3. The questions have been adapted from other assessments of psychosocial intervention satisfaction/acceptability in the literature. The estimated time to complete these items is 2 minutes.

4.3.5.9 Single-item Parent-child relationship quality assessment

Single item assessing participants' perceived relationship closeness with their child. This item is adapted from Sandler, et al. in their family intervention studies. We selected this item in lieu of longer measures to minimize participant survey burden. The estimated time to complete this item is no more than 1 minute.

4.3.5.10 Other resource use

Single item assessing participants' use of informal and professional resources with respect to their communication with their children (Appendix J). The estimated time to complete this question item is one minute.

4.3.5.11 Follow-up interview

Participants will participate in a semi-structured interview with a member of the study team to obtain feedback on the intervention (see Appendix K). If participants assigned to the treatment arm elect to withdraw prior to receiving the study intervention, they will remain eligible to participate in this interview. The post-intervention interview will occur face-to-face in a private room of NCCH, via telephone, or secure video. The interview is expected to take 30 minutes. Participants are not required to answer questions they find emotionally distressing and are reminded of this right before beginning the interview. All interviews will be audiotaped and then transcribed. Interview audio files and transcripts will be stored in a password-protected file within an electronic firewall-secured server maintained by the UNC School of Medicine. Audio files will be immediately uploaded post-interview and then immediately erased from the external audio recorder. Audio files will be completely erased at study closure.

4.3.6 Post-study Assessments

None. Participants who participate in this study will not be eligible for the anticipated randomized controlled trial that will formally test the efficacy of the intervention.

4.4 Compensation

Participants will be compensated for completing study assessments. Study compensation is structured such that participants will receive \$20 for completing T0, \$20 for completing T1 assessments, and \$20 for completing T2 survey assessments. Participants will also receive an additional \$20 for completing the semi-structured interview at T2 for a maximum total of \$80. In the event of early discontinuation, compensation will be pro-rated according to the above schedule.

4.5 Expected Risks

The primary risks in this study are a loss of privacy, loss of patient confidentiality, and the risk of emotional distress elicited during the interviews.

Loss of privacy

Approaching patients about enrollment in the clinic poses a risk to privacy. We expect this risk to be low. In the UNC ambulatory oncology clinics, research staff routinely approach patients for enrollment in clinical studies, and members of our team have completed prior survey and interview-based studies and psychosocial intervention clinical trials with careful attention to patient privacy and high acceptability on the part of participants. Approaching patients via telephone also poses a risk to privacy although we expect this risk to be low. Our research team has successfully approached patients about enrollment via telephone with attention to patient privacy and high acceptability on the part of participants.

Loss of confidentiality

Loss of confidentiality could occur if the study database was breached. This risk will be minimized with numerous steps to protect confidentiality (see Adequacy of Protection Against Risks, below). The alternative of not keeping identifiable information is not possible, because we will need to access the medical record to obtain illness information.

Risk of emotional distress

All eligible participants for this study will have or recently had a diagnosis of cancer – illnesses that are frequently associated with emotional, physical and spiritual distress. Eligible participants may be at higher risk for brief additional emotional discomfort or distress due to this study. Questions about communication concerns may be temporarily uncomfortable or distressing for some participants. We expect the risks of discomfort or distress to be low relative to the overall distress that the patients experience due to their serious illness. We have successfully conducted studies evaluating psychological distress, treatment decision-making, communication, prognostic understanding, and supportive care needs with parents with cancer. Participants with a wide range of educational backgrounds, illness severity, and psychological adjustment have described our study practices as appropriate and acceptable.

4.6 Adequacy of Protection Against Risks

Recruitment and informed consent

The research team will receive permission from the patient's oncology clinician(s) before approaching any eligible patients. As such, patients whom the oncology team believes are at high risk of emotional distress from study participation will not be approached. All participants will provide informed consent for the study and HIPAA authorization. Copies will be given to participants, and signed forms will be kept locked in the PI's office. When approaching an eligible patient, the research team member will describe the nature of the study questions and their purposes and written informed consent will be sought. For telephone recruitment, participants will provide study and HIPAA consent electronically through secure Qualtrics link. A copy of the consent form and HIPAA form will be emailed to participants who wish to retain a copy for their own records.

Participation in this study is voluntary. Patients who choose not to participate in this study will not be participant to prejudice in the delivery of health care by their physicians

and clinical staff nor by the research institution. The informed consent discussion will occur with a trained member of the research team. The informed consent process will include review of the purpose of the research, procedures, risks, benefits, and participant's rights. Study participants can contact the PI to address all questions both prior to and after consenting to participate in the study. All participants will be specifically reminded that they may withdraw at any time without impacting their treatment or relationship with their clinical team and that they may choose not to answer any study question they would rather not answer.

All members of the study team will undergo and maintain training in the responsible conduct of research.

Protection against loss of privacy

All study-related interactions will be conducted in private spaces at UNC Hospital or clinics or via telephone or secure video after ascertaining with the participants that their location is private. Per UNC IRB guidelines, we will use unencrypted communication (e.g., text messages) for survey reminders only if participants separately provide consent for this communication modality. We will use the UNC Transmission of Sensitive Information Standard's exception requirements for obtaining consent.

Protection against the risk of a loss of confidentiality

We will take several steps to mitigate this risk. All research staff will be thoroughly trained in the need to maintain strict confidentiality. Data will be reported in aggregate form only. All participants are assigned a unique study identifier and all participant-identifying information on paper will be kept in locked files accessible only to research staff. All electronic information will be password protected. No information obtained during the study will be used for any purpose other than the purpose for which the person has consented. The physical risks of the study procedures are minimal and the potential risks have been outlined above. The clinical care of any given participant will be handled entirely by the participant's oncologist, unless emergency care is needed due to suicidality (detailed below), and study participants will be made aware of this at the time of enrollment. Similarly, any medical problem that arises during study participation will be referred to the participant's oncology provider.

Only the research team will have access to identifiable information or to the study database. The study database will be password-protected and housed on a HIPAA-compliant, secure server at the NC TraCS Institute at UNC that are only accessible to IRB-approved personnel. The investigators and research staff will only access the database through encrypted, password-protected computers. Research staff will transport paper surveys and consent forms from the clinic to the locked office of the PI immediately after clinic and will conduct all data entry of pen-and-paper documents in the office. Surveys and consent forms will be kept in a locked cabinet in the locked office of the PI and will be destroyed upon study completion.

Protection against the risk of emotional distress or discomfort

When discussing the study with eligible patients, research staff will describe the nature of the study questions and intervention and their purposes. We will take several measures to reduce the risk of emotional distress that may occur in some study participants. First, as described above, a member of the research team will receive permission from a patient's oncology clinician before approaching them. As such, patients whom the treating oncology clinician believes are at high risk of emotional distress from study participation will not be approached. Second, research staff who have direct contact with participants will undergo training by the PI and Co-Investigator, [name], on how to assess and respond to participant distress. Both [name] are experienced mental health professionals who frequently provide clinical care for seriously ill patients with emotional distress. Third, participants complete measures of psychological distress, including the Patient Health Questionnaire-2 (PHQ-2) during the baseline and follow-up assessments.

In the unlikely event that a participant verbally endorses suicidality during study-related interactions, research staff will immediately contact the PI ([name] if she is unavailable). Fourth, if adverse events during or between study visits such as the unlikely event of severe emotional distress occur, they will be reported to the IRB by the PI—a board-certified psychiatrist with specialized training in psycho-oncology, and the participant's primary oncologist will be notified. Should research staff observe emotional reactions necessitating clinical intervention, the study participant will be offered support services in the form of psycho-oncology assessment by a trained member of the UNC CCSF psycho-oncology service which Co-Investigator, [name], oversees.

The PI will individually monitor the data continuously to ensure the safety of the participants. The PI will also monitor data through weekly meetings with research staff and monthly group meetings of key study personnel. This trial will be audited by the LCCC every six to twelve months per the audit committee's guidelines and assigned a LCCC Data Safety Monitoring Committee (DSMC) per Lineberger guidelines.

4.7 Removal of Patients from Protocol

Participants will be removed from the study when any of the criteria listed in Section 3.2 apply or the participant elects to withdraw from the study. If this occurs, the PI will be notified and the reason for study removal and the date the participant was removed will be documented in the Case Report Form.

In order to support the statistical integrity of analyses, the pre-randomization discontinuation of any participant will trigger the recruitment and enrollment of an additional participant. Participants who discontinue after randomization will not be “replaced” in this manner.

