2.2 Secondary Objective

A secondary objective of this study is to evaluate the feasibility of the study and study procedures in preparation for a future efficacy RCT of the intervention. We will report on participant screening, recruitment, and retention.

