3.2 Exclusion Criteria

Eligible participants must not have any of the following to be enrolled in the study.

- 3.2.1. Unable to complete self-report instruments due to illiteracy, neurologic illness, inability to speak or read English, or other causes;
- 3.2.2. Prior participation in the pilot trial (LCCC2030) or development and user testing protocol (LCCC1952) preliminary to this study;
- 3.2.3. No current or expected contact with their child; or
- 3.2.4. Existence of other co-morbid disease, which in the opinion of the investigator, prohibits participation in the protocol.

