4.3.2.2 Randomization

Participants will be randomized to one of two arms: (1) intervention arm, or (2) control arm. Participants will be assigned with an allocation ratio of 1:1 and stratified by disease status: advanced (stage IV or equivalent) vs non-advanced. This will be implemented through REDCap's randomization module which will directly follow entry of baseline data. Setup of the randomization module will be done only by the PI or CRC, and the study biostatistician will confirm that the randomization scheme logic is functional before any data is collected. This logic will be preserved such that group assignment cannot be altered or manipulated when accrual begins.

Given the nature of this study, a double-blind design is not possible as both the participants and recruiting staff will be able to easily infer group assignment.

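### Section 4.7 applies the entry exclusion criteria without a time limit, so randomised participants who later meet one must leave the study and their remaining data are lost

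*Combined protocol and SAP*

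**What the plan says.** Section 4.7 gives two grounds for leaving the study. The first is a rule: "Participants will be removed from the study when any of the criteria listed in Section 3.2 apply". The second is the participant's own choice to withdraw. The reason and date of removal go on the Case Report Form. The next paragraph deals with replacement: "the pre-randomization discontinuation of any participant will trigger the recruitment and enrollment of an additional participant", whereas "Participants who discontinue after randomization will not be" replaced.

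Section 3.2 is worded as a list of entry exclusions. Criterion 3.2.1 reads "Unable to complete self-report instruments due to illiteracy, neurologic illness, inability to speak or read English, or other causes". Criterion 3.2.3 is having no present or foreseen contact with the child. Criterion 3.2.4 reads "Existence of other co-morbid disease, which in the opinion of the investigator, prohibits participation in the protocol". Criterion 3.2.2, earlier participation in the preliminary studies, is fixed at entry and matters later only if it is discovered late.

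On blinding, Section 4.3.2.2 says that "both the participants and recruiting staff will be able to easily infer group assignment". Section 4.6 has the principal investigator reviewing data continuously. No blinded person is assigned to decide on removal.

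On use of the data:
- Section 2.2 (secondary objective): "We will report on participant screening, recruitment, and retention".
- Section 7.1: the intervention goes forward if at least 75% rate it acceptable.
- Section 7.3.1: that rate is reported at T1 with an exact interval.
- Section 7.3.4: the CSES results of this pilot will supply the effect size for the next trial.

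No section defines an analysis set or a missing-data rule.

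**The concern.** Criteria written to decide who may enter are reused to decide who must leave. Before randomisation this does no harm, because the participant is replaced. After randomisation it creates exclusions that are not replaced and that depend on events during follow-up.

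The population has stage II-IV solid tumours and is not in surveillance or survivorship, so a new incapacity, a change in contact with the child or a new co-morbidity within about six weeks is plausible. The rule removes the person from the study, not only from the intervention. Someone who cannot manage written surveys might still give a telephone interview at T2, and record abstraction asks nothing of the participant. Both stop.

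Three results are exposed: the T1 acceptability rate, which feeds the 75% rule; retention; and the exploratory CSES change.

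**Working it through.** **Does the rule reach randomised participants?** Four texts, taken together:

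1. Section 4.7 makes removal mandatory and gives no time limit.
2. The same section goes on to discuss participants who discontinue after randomisation, so it is not confined to screening.
3. In Section 5.1, T1 is at day 21 (±14) and T2 at day 42 (±14). Surveys and record abstraction fall at both, and the interview at T2. A criterion first met after day 0 therefore removes whichever of these remain.
4. The only follow-up offered after leaving is in Section 4.3.5.11. It is limited to the interview, for FACT-arm participants who choose to withdraw before receiving FACT. It does not cover removal under Section 3.2.

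So the rule does reach randomised participants, by the absence of a limit rather than by an explicit statement.

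**The plan's own figures.** Section 7.2 gives an exact (Clopper-Pearson) 95% interval of 50.9% to 91.3% for a 75% rate with n = 20, and a half-width of no more than 23 points. For 15/20 the recomputed interval is 50.9% to 91.3%. The largest half-width at n = 20 is 22.8 points, at 10/20. Both figures reproduce.

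**Illustration of selection into the T1 rate.** Inputs:
- N = 20 randomised to FACT: the 40 of Sections 1.1 and 4.1, at the 1:1 allocation of Section 4.3.2.2 (40/2 = 20).
- The 75% rule of Section 7.1.
- k participants removed before T1. This is an assumption; the documents give no removal rate.

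Formulas:
- Fewest acceptable ratings that meet the rule: r = 0.75 × (N − k), rounded up.
- Observed rate: r/(N − k).
- Range over all randomised: r/N if every removed participant would have rated FACT not acceptable, (r + k)/N if every one would have rated it acceptable.

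| k | N − k | r | Observed | Over all 20 |
|---|---|---|---|---|
| 2 | 18 | 14 | 14/18 = 77.8% | 14/20 = 70% to 16/20 = 80% |
| 4 | 16 | 12 | 12/16 = 75.0% | 12/20 = 60% to 16/20 = 80% |
| 6 | 14 | 11 | 11/14 = 78.6% | 11/20 = 55% to 17/20 = 85% |

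**The larger sample size.** Section 7.2 speaks of recruiting 55, or 27 to 28 per arm (55/2 = 27.5). With k = 4:
- N = 27: 18/23 = 78.3% observed, against 18/27 = 66.7% to 22/27 = 81.5% over all randomised.
- N = 28: 18/24 = 75.0% observed, against 18/28 = 64.3% to 22/28 = 78.6%.

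The pattern does not depend on which sample size is meant.

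**The case against.** The strongest reply is that the rule will seldom bite and that little is lost when it does. A participant who truly cannot complete the instruments supplies no survey scores under any rule. The primary rate is measured in the FACT arm only, and Section 7.3.4 says the study is neither designed nor powered to detect differences. These points stand, and they limit the size. They do not cover an incapacity that resolves before T2, the T2 interview, record abstraction, or a participant removed under 3.2.3 or 3.2.4 who could still answer.

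Four stronger readings are tempting, and the documents do not support them:

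- **A missed T1 survey leads to removal.** It does not. Criterion 3.2.1 describes inability, and Section 4.3.5 lets participants complete some or all of the surveys and skip questions.
- **Removal by the team and loss to follow-up become indistinguishable.** They do not. Reason and date of removal are recorded, and Section 7.3.3 describes those who enter, remain and drop out. What is missing is a plan to report removals separately and a retention denominator of all randomised; Section 7.3.3 frames its percentages among patients approached.
- **The stated precision fails.** The n = 20 of Section 7.2 counts hoped-for T1 completers out of 55 recruited, so it already allows for attrition. The largest half-width would be 23.3 points at 19 completers but 20.9 at 24. Precision suffers only if about 20 are randomised to FACT.
- **Sicker patients are lost, and the arm contrast is biased by unblinded judgement.** This is inference. Criterion 3.2.4 concerns other co-morbid disease, not progression of the cancer. Section 4.3.2.2 names participants and recruiting staff as able to infer the arm and does not say who decides on removal. No difference in removal between arms can be derived from the documents.

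**Conclusion.** The point holds as a defect in a stated rule with a cheap remedy. Followed as written, Section 4.7 excludes randomised participants who come to meet 3.2.1, 3.2.3 or 3.2.4, and ends data collection that could otherwise continue. These exclusions may be related to health or family situation and, under 3.2.4, rest on judgement in an open trial.

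The size cannot be estimated, because no removal rate is given. Under the assumption of 4 removals among 20 FACT participants before T1, a rate that just meets the 75% rule is compatible with 60% to 80% over everyone randomised to FACT. That is a bound on what could be hidden, not a forecast. The effect on the CSES change is of unknown size and concerns an exploratory result, though one intended to size the next trial. This is a low-cost improvement, not a flaw that invalidates the pilot.

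**What to change.** **Section 4.7.** State that Section 3.2 is applied as eligibility criteria up to randomisation only. After randomisation, continue to offer the scheduled surveys and interview unless the participant withdraws consent or can no longer take part. Record each missed assessment with its reason.

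**Section 7.3.** Report retention and the arm comparison over all randomised participants, in the arm to which they were randomised. List removals by arm and reason. Beside the T1 acceptability rate among those who rated FACT, show a sensitivity analysis in which FACT participants without a T1 rating count as not acceptable.

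**Cost.** Short edits to two sections and some additional missing-data reporting. No new visits are needed, since the assessments are already scheduled and participants may already skip questions.
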